1.1. Summary and objectives of the study

The aim of this 24-month study is to evaluate the effectiveness and cost-effectiveness of emergency surgery for common acute conditions such as appendicitis, that present as emergency admissions to NHS hospitals. The 'intervention' strategy is emergency surgery within the index hospital episode, and the 'comparator' strategy is non-operative care including: 'medical management', a 'non-surgical' procedure, and the possibility of subsequent planned (elective) surgery.

The specific objectives are to evaluate the:

1. effectiveness of emergency surgery versus non-operative care for common acute conditions presenting as emergency admissions across broad ICD-10 categories.
2. relative cost-effectiveness of emergency surgery versus non-operative care across broad ICD-10 categories.
3. clinical and cost-effectiveness of operative versus non-operative care for specific patient subgroups, including diagnostic subcategories and patient characteristics.

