1.2. Overview of methods

The study will apply an instrumental variable (IV) design that can fully address confounding and provide accurate estimates of treatment effectiveness even when there are unmeasured differences between the comparison groups, for example in patient case-mix. This study will extend the IV design developed by a co-applicant ([name]) that used surgeon's tendency to operate (TTO) to evaluate emergency surgery versus non-operative strategies in the United States (US)¹. We will apply this IV design to Hospital Episode Statistics (HES) database extracts from 2009-2020. Our preparatory work using an extract of HES data (2014-5), found that the essential assumptions behind the IV design were realistic, in that the TTO, predicted the receipt of emergency surgery, and was unlikely to directly affect the outcomes.

We have chosen to include five acute conditions with well-defined intervention and comparator strategies where there is clinical uncertainty, and wide variation in the receipt of emergency surgery across the NHS. Focusing on these conditions will help ensure this research can inform future clinical guidelines and service provision. We will define final inclusion criteria for each condition as part of the proposed research, and in consultation with a multidisciplinary clinical panel.

The main outcomes are: mortality at 30 days and one year after the index emergency admission, hospital re-admission, and days alive and out of hospital up to 30 days after the index admission. The final choice of outcomes will be informed by a PPI 'study design' workshop.

The cost-effectiveness analyses (CEA) will use resource use data and mortality data from HES and the Office for National Statistics (ONS), and health-related quality of life (HRQoL) estimates from the literature. We will report the relative effectiveness and cost-effectiveness of emergency surgery for each acute condition. We will apply a local IV approach², to report results for pre-specified subgroups of policy relevance including patient demographics, comorbidities and route of admission. The study will provide future commissioners of acute services and of research, with evidence on those patient subgroups for which emergency surgery is relatively cost-effective, those for whom non-operative strategies are more worthwhile and those where further research is warranted.

This project is funded by the NIHR Health Services Research and Development Programme.

2. Project Overview

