2.2. Research plan/methods

2.2.1. Methods

Overview

The study will estimate the effectiveness and cost-effectiveness of emergency surgery versus non-operative strategies for common acute conditions that present as emergency admissions to NHS hospitals in England. We will define the target population from emergency admissions within a single data source (HES) to ensure consistent definitions, for example of inclusion criteria, across the patient cohort. The target population will include five acute conditions that present as emergency hospital admissions: appendicitis, cholecystitis, diverticulitis, acute symptomatic hernia, intestinal obstruction. The 'intervention' strategy is defined as emergency surgery within the index hospital episode, and the 'comparator' strategy as non-operative care or 'watchful waiting' within that episode which could include: 'medical management', a 'non-surgical' procedure, and then possibly subsequent planned (elective) surgery.

For each acute condition, the specific definitions of the study population, intervention and comparator will be refined at an early stage of the planned research. The initial definitions of the populations (P), interventions (I) and comparators (C) will be developed with the full HES dataset (phase 1). These initial definitions will be presented to a clinical panel, and then refined through structured discussion. The refined PIC definitions will be applied to the HES dataset, presented to a virtual clinical panel, and finalised (phase 2).

The study will access linked data for emergency hospital admissions from HES and the ONS (data request submitted April 2018; approved 20 September 2018; revised request submitted May 2020; expected data receipt, Sept 2020). We will collate information on diagnosis (ICD-10), case mix, surgical procedures received, resource use and outcomes, including mortality.

Instrumental variable design

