Exclusion criteria for defining the *index admission* will include: age less than 18, a previous emergency admission for the condition within the year prior to the index admission, referrals from tertiary referral centres (see IV assumptions below), and any additional exclusion criteria deemed appropriate by the clinical panel, for example minimum surgical volume thresholds for a particular hospital.

Table 1: Exemplar acute conditions, interventions and comparator strategies, and trust-level tendency to operate (TTO), from pilot HES data (2014-5)

Acute condition ¹	Population ² (estimated cohort 09-18)	Intervention ³	Comparator ³	NHS Trust TTO ⁴ median (IQR)	F statistic ⁵
Appendicitis	333,000	Appendectomy	Supportive care; Antibiotic treatment	89.3% (84.9%, 92.8%)	114
Cholecystitis	422,000	Cholecystectomy	Delayed cholecystectomy	17.3% (11.2%, 25.0%)	65
Diverticulitis	224,000	Resection; Colectomy; Laparoscopic lavage	Antibiotic therapy; intravenous fluid therapy Percutaneous	9.0% (6.6%, 10.9%)	678

			drainage of abscess		
Acute symptomatic hernia ⁶	70,000	Repair of hernia	Watchful waiting; Delayed repair of hernia	46.7% (39.4%, 58.7%)	148
Intestinal obstruction (small or large bowel)	235,000	Adhesiolysis; Colonic stenting; Bowel resection	Watchful waiting with intravenous fluid	29.9% (25.5%, 34.3%)	931

¹Acute condition refers to pathology and ensuing complications. The clinical panel will define specific complications related to pathology for the final inclusion criteria ²Population defined by ICD-10 codes. ³Intervention and elective surgery comparators are defined by OPCS codes. ⁴Percentage of the eligible population with an intervention within index HES episode. ⁵From Cragg-Donald weak identification test. ⁶Includes inguinal hernia, femoral and incisional.

Intervention

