For each acute condition, surgical intervention is defined as an operative procedure corresponding to one of a pre-determined set of OPCS Classification of Interventions and Procedures codes within the index emergency admission. Table 1 includes examples of typical procedures or treatments for each acute condition. Code lists will be refined during the initial phase of the research (see later section for further details). Final criteria for defining a relevant surgical intervention will recognise the timing of surgery with respect to hospital admission, and its relationship with other surgical and non-surgical procedures within the admission. These final criteria will stipulate what delay to surgery is required for it to meet the criteria for a 'comparator' rather than 'an intervention strategy'. Alternative specifications will be considered in sensitivity analyses.

Our preparatory work has identified an extensive list of provisional OPCS procedure codes that indicates the patient has had a surgical intervention. Exemplar procedures include: H01.2 Emergency excision of abnormal appendix (appendicitis); J18.3 Total cholecystectomy (cholecystitis); T20.2 Primary repair of inguinal hernia using insert of prosthetic material (inguinal hernia); H33.5 Rectosigmoidectomy and closure of rectal stump and exteriorisation of bowel (diverticular disease); T41.3 Freeing of adhesions of peritoneum (intestinal obstruction).

Comparator strategy

For each acute condition, the comparator is defined as an eligible admission whose care does not include an operative procedure considered to constitute the intervention. This includes patients receiving non-surgical treatment or diagnostic evaluation as identified by OPCS codes, and those with no procedure recorded during their index admission. The comparator strategies include delayed surgery, defined as having a relevant surgical procedure but after the specified time-frame for the intervention.

Case mix and potential confounders

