Information from HES on patient characteristics will be available at the patient-level and will comprise socio-demographic characteristics (age, sex, ethnicity and decile group of the index of multiple deprivation). Comorbidities will be derived using HES records from all admissions for each patient in the year prior to and including the index admission using the RCS Charlson score²⁹. The definition of co-morbidities will use both information on past medical history according to chronic conditions, but also according to reasons for previous admissions. Potential higher-level confounders will include surgical volume for relevant emergency and elective procedures for each acute condition. These surgical volumes will be calculated for each financial year from 2008-09 to partial 2020-21 using HES records for all relevant patients. We will report these measures of volume at the levels of the consultant surgeon, hospital (including surgical team), and NHS trust.

Outcomes

The main outcomes will be mortality at 30 days, 90 days and one year after the index emergency admission, readmissions, and days alive and out of hospital prior to 30 days. For each index emergency admission, we will access information on mortality, re-interventions and readmissions (including emergency and elective surgery) from HES and ONS data. Further surgery within 30 days and one year will be defined according to OPCS intervention codes. Readmission will be defined as any hospital admission within one year of the index admission, subdivided according to emergency versus elective, including for planned (re)intervention. The definition of mortality at 30 days, 90 days and one year following the index admission will be according to indicators provided by NHS Digital and will use ONS date of death. We will also have access to date of death through ONS linkage, and will calculate the number of days alive and out of hospital before day 30. We will convene a Patient and Public workshop (Design Workshop 2) to discuss the study outcomes (see PPI section for full details).

Missing and miscoded data

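### Days alive and out of hospital, a main outcome, closes at day 30 and so leaves out later planned surgery that belongs to the comparator strategy

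*Protocol*

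**What the plan says.** Section 1.2 names "days alive and out of hospital up to 30 days after the index admission" as a main outcome. Under Objective 1 in section 2.2.2, the Outcomes text repeats this as "days alive and out of hospital prior to 30 days" and adds that the team "will calculate the number of days alive and out of hospital before day 30". No longer window is given for this outcome.

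The comparator is described as a strategy. Section 1.1 includes in it non-operative care "and the possibility of subsequent planned (elective) surgery", and section 2.2.1 says "and then possibly subsequent planned (elective) surgery". The Comparator strategy text of section 2.2.2 states: "The comparator strategies include delayed surgery, defined as having a relevant surgical procedure but after the specified time-frame for the intervention". It sets no upper time limit. In Table 1, "Delayed cholecystectomy" is the only comparator listed for cholecystitis, and "Delayed repair of hernia" is one of two listed for acute symptomatic hernia.

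The remaining outcomes run longer. In the Outcomes text, mortality is taken at 30 days, 90 days and one year, readmission to one year with emergency and elective admissions separated, and further surgery at 30 days and one year. Under Objective 2, costs and QALYs run to one year and costs include delayed surgery.

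**The concern.** The stated question compares two strategies. The emergency operation takes place in the index admission, so its stay begins inside the 30-day window. The planned operation that forms part of the comparator may take place after the window has closed, and then it adds no hospital days to that group. The outcome therefore covers the defining procedure of one strategy but not necessarily that of the other.

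This matters because mortality, readmission and this measure are the main outcomes of Objective 1, and only this one puts death and time in hospital on a single scale. A reader is likely to take it as the net result for the patient. If much of the comparator's planned surgery falls after day 30, part of an apparent gain in days at home is a deferral of hospital days beyond the point of measurement.

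**Working it through.** The protocol gives no effect size, standard deviation or power for this outcome. The Sample size text concerns an absolute risk difference. There is therefore no planned figure to reproduce, and the check is an account of bed-days.

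**Inputs from the protocol**
- Window: 30 days from the index admission (section 1.2; section 2.2.2, Outcomes).
- Emergency surgery: within the index admission (section 2.2.2, Intervention).
- Delayed surgery: part of the comparator, no upper time limit (section 2.2.2, Comparator strategy).
- Conditions with delayed surgery named in Table 1: cholecystitis (estimated cohort 422,000) and acute symptomatic hernia (70,000). The five cohorts sum to 333,000 + 422,000 + 224,000 + 70,000 + 235,000 = 1,284,000, so these two make up 492,000 / 1,284,000 = 38%.

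**Inputs not in the protocol (assumed)**
- p: share of comparator patients with planned surgery after day 30; D: its bed-days.
- q: share of emergency-surgery patients with a readmission or re-intervention after day 30; R: its bed-days. Strictly, q × R should be the excess over comparable late unplanned stays in the comparator group.
- Deaths after day 30 and index stays running past day 30 are ignored.

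**Formula**, with each difference taken as surgery minus comparator:

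shift = (difference at one year) − (difference at 30 days) = p × D − q × R

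A positive shift means that the 30-day window is more favourable to non-operative care than the one-year window.

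**Comparator bed-days left out, with q × R = 0**
- p = 10%, D = 1: 0.10 × 1 = 0.1 day
- p = 50%, D = 2: 0.50 × 2 = 1.0 day
- p = 70%, D = 4: 0.70 × 4 = 2.8 days

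**Effect on a result.** Assume index stays of 6 days (surgery) and 4 days (non-operative). The 30-day difference is (30 − 6) − (30 − 4) = −2.0 days. The one-year difference is −2.0 + p × D − q × R:

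| p | D | q | R | p × D | q × R | One-year difference |
|---|---|---|---|---|---|---|
| 10% | 1 | 0 | – | 0.1 | 0 | −1.9 |
| 50% | 2 | 0 | – | 1.0 | 0 | −1.0 |
| 70% | 4 | 0 | – | 2.8 | 0 | +0.8 |
| 50% | 2 | 5% | 5 | 1.0 | 0.25 | −1.25 |
| 10% | 8 | 30% | 8 | 0.8 | 2.4 | −3.6 |

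In the third row the sign reverses in favour of surgery. In the last row, with frequent late re-intervention after surgery and rare planned surgery in the comparator, the 30-day window is the one that flatters surgery. The sign of the shift therefore depends on quantities that the protocol does not supply.

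**The case against.** The strongest reply is that the later events are already covered. Readmission is itself a main outcome, runs to one year and separates elective from emergency admissions. Further surgery is defined to one year. Objective 2 counts one-year costs including delayed surgery and joins them to QALYs in the incremental net monetary benefit, so a one-year measure reflecting both death and later hospital use does exist. This stands as partial cover. But readmission and further surgery are reported apart from death, and net monetary benefit is an economic measure that does not tell a patient how many days were spent alive and at home.

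A second reply is that 30-day days alive and out of hospital is a well-defined short-term quantity, openly labelled with its horizon. That is correct. A reader might infer that the 30-day estimate is biased. Nothing in the protocol shows this; the difficulty is that the horizon does not fit the strategies being compared.

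Third, a reader might infer that the window captures every bed-day of emergency surgery and so always favours non-operative care. The protocol does not support that. Stays after day 30 are cut off in both groups, and the Resource use and unit costs text expects re-interventions in either group. Table 1 names no delayed surgery for appendicitis, diverticulitis or intestinal obstruction. Some delayed surgery may also fall within 30 days, since the time-frame separating intervention from comparator is still to be set.

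Finally, the choice of outcomes is provisional until the patient and public workshop. That makes a change easy, but it is no reason for the 30-day limit. Uncertainty about direction is likewise a reason to measure for longer.

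**Conclusion.** The point stands in a limited form. A main outcome stops before the comparator strategy is complete, and it is the only Objective 1 outcome that combines death with time in hospital. For cholecystitis and acute symptomatic hernia the omission is likely to favour non-operative care, provided that a material share of the planned operations falls after day 30 and is not outweighed by late stays after emergency surgery. For the other three conditions no direction can be claimed.

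The range of 0.1 to 2.8 days per comparator patient rests wholly on assumed shares (10% to 70%) and assumed bed-days (1 to 4), and is stated before any offset. It shows that the omission could matter, not that it will. The high proportion of non-operated patients in cholecystitis (100 − 17.3 = 82.7% at the median trust in the pilot data) does not enlarge it, because the measure is a difference per patient between strategies. Given the partial cover from the one-year outcomes, this is a worthwhile and inexpensive improvement rather than a flaw that invalidates the study.

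**What to change.** In section 1.2 and in the Outcomes text of section 2.2.2, define days alive and out of hospital at 90 days and at one year, matching the mortality time points in the Outcomes text (section 1.2 currently omits the 90-day one). Base the comparison of strategies on these longer windows and label the 30-day version a short-term measure. Both longer windows are needed: the protocol gives no timing for planned surgery, so 90 days alone might still cut some of it off. Make the change while the choice of outcomes is still open and before outcome data are analysed.

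No new data are needed, since HES admissions to one year and ONS dates of death are already planned. The work is a change of wording and minor programming. The costs are somewhat more non-specific variation over a longer window, and a need for the same follow-up of index admissions that one-year mortality already requires.

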The critical challenge for any non-randomised study is that there are liable to be potential confounders that are not observed. While we could apply traditional risk adjustment approaches, the major problem is that HES does not contain detailed measures of patient physiology, or prognostic measures such as frailty that are likely to influence the choice of operative versus non-operative care, and outcome. Hence, risk adjustment methods would be likely to provide biased estimates of the effectiveness of operative versus non-operative care. We therefore propose an IV study design^{1,25,26}. A valid IV design can provide accurate estimates of treatment effectiveness even when there are unmeasured differences between the comparison groups^{25,26}. An IV encourages receipt of the treatment, in this case emergency surgery, but does not have a direct effect on the outcome, for example 30-day mortality, except through treatment receipt.

Our study will use an IV developed and validated by [name] et al (2018) for evaluating emergency surgery in the US. The precedent study covered 50 acute conditions including the five that we will consider in the proposed study. The IV for the receipt of surgery is the TTO defined as the propensity of an individual (e.g. surgeon) or unit (e.g. surgical team, hospital or trust) to use operative versus non-operative management¹. [name] et al (2018) found that TTO was a valid IV in that it varied widely across surgeons and was not correlated with surgical skill or experience¹. We will use TTO as an IV to estimate the relative effectiveness and cost-effectiveness of emergency surgery versus comparator strategies in the NHS while minimising bias from unobserved confounding.

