The main potential issues are missing values for case mix variables and failure to record diagnoses, procedures or outcomes. Missing or unreported ethnicity data in eligible admissions (c10%), and deprivation (c1%) will be minimised by using ethnicity and deprivation data from patients' other linked episodes. HES data for age and sex are almost complete. We will recognise the potential impact of improvements in the coding of diagnoses in HES between 2008-2020 by including a covariate for financial year in the analysis models. We will examine the use of diagnosis/procedure codes over time periods to identify other potential issues that need to be considered in defining PICO criteria, for example expanding eligibility to include secondary as well as primary diagnoses. For any missing covariate data, we will make plain any assumptions that we do make, drawing on previous work from ourselves and our collaborators. For example, for baseline covariates with missing values we will examine whether this pattern of missingness differed across the intervention and comparator groups. We will use the approach recommended by Rosenbaum (2010) to making minimal, but transparent assumptions about the missing data while balancing patterns of missingness across intervention and control groups³⁰.

Instrumental variable

Our proposed IV design follows research in pharmaco-epidemiology²⁶ that uses provider preference as an instrument for treatment receipt. In this study, the IV will be the TTO, defined for each acute condition, as the proportion of emergency admissions during which an eligible surgical procedure is undertaken. Hospitals and surgeons will be identified from the HES provider/site of treatment codes, and the consultant/specialty codes as in precedent research by the applicants^{1,30}. In the primary analysis, TTO will be defined at the hospital-level, to recognise that in the NHS, multidisciplinary team input informs the decision to operate. We will also report sensitivity analyses with TTO defined at the trust-level, as in the pilot data, and at the consultant-level, for comparison with the precedent study¹. We will calculate TTO by financial year (2008-09 to partial 2020-21) using HES records for all relevant patients.

Sample size

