In the HES pilot data, we found that the trust-level TTO was strongly associated with receipt of emergency surgery; for each condition the F-statistics exceeded the critical value of 10, and therefore assumption i) was satisfied (see Table 1)³¹. We will repeat these tests of instrument strength for the full HES data for each level of the TTO. For assumption ii) we found that the trust-level TTO balanced the observed covariates, and we will explore this further in the full HES data^{32,33}. Although we cannot assess empirically whether TTO is independent of unmeasured confounders, in the emergency setting this assumption is likely to be justified for hospitals, since the vast majority of patients will attend their local hospital without consideration of the hospital-level TTO. This assumption will be bolstered by the exclusion of patients referred to tertiary referral centres for whom this assumption is less plausible. These patients can be identified from HES data on admission source, and distance to provider. For assumption iii) it seems unlikely that after adjusting for the volume of EGS and the outcomes of previous admissions, that the TTO would have a direct effect on the outcomes. For example, it is unlikely that just because a surgical team prefers to operate, that the patients' outcome would be better (or worse) unless that patient actually underwent an operation. We will use falsification tests to probe the plausibility of assumptions (ii) and (iii). Specifically, we will identify subgroups where all patients receive emergency surgery, and test whether the TTO has an effect on outcomes in these subgroups^{34,35}.

Most IV applications also assume that there are 'no defiers' – patients treated contrary to the physicians' preference^{33,36}. Here, this implies that there are no patients who receive surgery simply because they present in a high TTO hospital and vice versa. Following the approach of Swanson et al. (2015)³⁷ for checking the assumption of 'no defiers', we will survey the clinical panel about their preferences and choice of strategy for a set of hypothetical patients with the above acute conditions using vignette patient profiles. This will allow us to assess the magnitude and direction of any bias due to the presence of no defiers.

Estimation and sensitivity analyses

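### Attending the local hospital rules out choosing it for its TTO, but not prognostic differences between catchments, and no analysis stated in the protocol isolates a within-hospital contrast

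*Protocol*

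**What the plan says.** All references are to the Protocol; section 2.2.2 holds the Objective 1 methods.

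- **Instrument (2.2.2, Instrumental variable).** TTO is defined per condition "as the proportion of emergency admissions during which an eligible surgical procedure is undertaken". No case-mix adjustment of that proportion is stated. On timing: "We will calculate TTO by financial year (2008-09 to partial 2020-21) using HES records for all relevant patients".
- **Level (same place).** "In the primary analysis, TTO will be defined at the hospital-level". The other levels are "sensitivity analyses with TTO defined at the trust-level, as in the pilot data, and at the consultant-level, for comparison with the precedent study". None is described as conditional on hospital or region.
- **Independence (2.2.2, Checking IV assumptions).** "Although we cannot assess empirically whether TTO is independent of unmeasured confounders", the assumption is called likely for hospitals because "the vast majority of patients will attend their local hospital without consideration of the hospital-level TTO". Excluding patients referred to tertiary centres is offered as further support.
- **What is unmeasured (2.2.1, Instrumental variable design).** HES lacks detailed physiology and "prognostic measures such as frailty that are likely to influence the choice of operative versus non-operative care"; the same sentence says these also affect outcome.
- **Safeguards (2.2.2).** These are observed-covariate balance (found for trust-level TTO in the pilot); age, sex, ethnicity, deprivation decile and comorbidity as case-mix variables; adjustment for surgical volume and previous admissions' outcomes; falsification tests in subgroups where everyone is operated on; nonparametric bounds; and a sensitivity analysis for an unobserved confounder of instrument and outcome.
- **Hospital as a grouping.** Under Objective 3 it enters as clustering in the standard errors.

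**The concern.** Two different things could link TTO to prognosis. One is selection: patients, or those who refer them, pick a hospital because of how readily it operates. Local attendance is a good argument against that. The other is composition: hospitals serve populations that differ in frailty or in severity at presentation. Local attendance is no argument against that, because it fixes each hospital's case mix as that of its area.

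Crude TTO is computed from those same patients. If unmeasured frailty or severity influences individual decisions to operate, as the protocol says it does, its average level in a catchment can shift the hospital's proportion operated on and its mortality together. The instrument would then carry, in aggregate, some of the confounding it is meant to remove.

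The hospital-level result is the primary effectiveness estimate, and hospital TTO also drives the person-level estimates under Objective 3. An IV estimate divides any residual imbalance by the difference in treatment rates, so a small imbalance can become a large bias.

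**Working it through.** The protocol gives no figure for this bias, so there is none to reproduce. The steps below gauge its possible size.

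**1. Formula.** Compare hospitals at the upper and lower TTO quartiles. Let D be the difference in proportion operated on, d the residual difference in baseline risk between their catchments after adjustment, and b a constant true effect. The outcome difference is b × D + d, so the IV ratio is b + d/D. The bias is d/D.

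**2. Inputs.** D is the interquartile range of trust-level TTO in Table 1 (pilot, half of acute trusts, 2014-15). The values of d are assumptions, shown as a range. Signs are omitted because the direction is unknown.

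| Condition | D | Bias if d = 0.1 | d = 0.2 | d = 0.5 | d giving 5 points |
|---|---|---|---|---|---|
| Hernia | 58.7 − 39.4 = 19.3 | 0.5 | 1.0 | 2.6 | 0.97 |
| Cholecystitis | 25.0 − 11.2 = 13.8 | 0.7 | 1.4 | 3.6 | 0.69 |
| Obstruction | 34.3 − 25.5 = 8.8 | 1.1 | 2.3 | 5.7 | 0.44 |
| Appendicitis | 92.8 − 84.9 = 7.9 | 1.3 | 2.5 | 6.3 | 0.40 |
| Diverticulitis | 10.9 − 6.6 = 4.3 | 2.3 | 4.7 | 11.6 | 0.22 |

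All entries are percentage points; for example 0.1/0.043 = 2.3, and 5 × 0.043 = 0.22. The 5-point benchmark is the difference in the sample size section, which names no outcome.

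**3. Do the planned TTO levels separate catchment from preference?** A simulation with true effect zero assumed 150 hospitals, 8 consultants each and 150 patients per consultant. TTO had SD 9 points between hospitals and 6 points between consultants within a hospital. Mortality was 6%, changing by 1 point per SD of unmeasured catchment severity. TTO was taken from one half of the patients and the other half was analysed. Patients reached consultants independently of severity, by construction. Mean IV estimates over 200 runs, in points:

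| Correlation of severity with hospital TTO | Hospital TTO | Consultant TTO, no hospital effect | Consultant TTO within hospital |
|---|---|---|---|
| 0 | 0.0 | 0.1 | 0.1 |
| 0.3 | 3.1 | 2.3 | −0.1 |
| 0.5 | 5.3 | 3.9 | 0.2 |

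Without conditioning on hospital, consultant TTO keeps much of the between-hospital bias, though not all. If there is no correlation there is no bias.

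**4. Can a same-year consultant TTO be used for the within-hospital contrast?** Section 2.1 gives about 4,000 consultants. Over the nine years of the Table 1 cohorts that is 4,000 × 9 = 36,000 consultant-years. Patients per consultant-year (m) are 70,000/36,000 = 1.9 for hernia, 6.2 for diverticulitis, 6.5 for obstruction, 9.3 for appendicitis and 11.7 for cholecystitis.

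If the patient's own treatment is included, the share of the first stage that is sampling noise is [p(1 − p)/m] / [s² + p(1 − p)/m]. Here p is the Table 1 median TTO and s is the SD between consultants, assumed to be 0.06 as in step 3.

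- Hernia: 0.249/1.94 = 0.128; 0.128/(0.0036 + 0.128) = 97%.
- Appendicitis: 0.0956/9.25 = 0.0103; 0.0103/(0.0036 + 0.0103) = 74%.
- The other conditions lie between. If only half of the consultants treat a given condition, m doubles and the range becomes 59% to 95%.

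That share of the estimate is the ordinary confounded comparison of operated and non-operated patients. The within-hospital analysis therefore needs a TTO that excludes the patient's own treatment.

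**The case against.** **The protocol does not ignore unmeasured confounding.** It says independence is untestable, calls it only likely, and plans falsification tests, bounds and an unobserved-confounder analysis. The last is close to the scenario raised here. This stands, and a reader who inferred that the threat is unaddressed would be wrong. But these checks show how fragile an estimate is; they do not remove a catchment difference. The falsification test may also lack power. Detecting a 0.2-point difference with 80% power at two-sided 5% needs 7.85 × 2 × p(1 − p)/0.002² patients per group, which is about 39,000 at 1% mortality and 353,000 at 10% (both mortality rates assumed, clustering ignored). For diverticulitis, 9.0% of 224,000 gives about 20,000 operated patients in all. Appendicitis has far more operated patients, so the test may be more informative there.

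**Model terms may sit in an analysis plan.** The timetable says analysis plans are published separately, so the absence of hospital or region effects from the protocol is not itself an error. This stands. What remains is the inference the protocol does state.

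**Observed balance and covariates help.** They do, for measured factors. They do not reach the physiology and frailty that the protocol says are missing.

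**A direction might be inferred:** surgeons operate less on frail patients, so low-TTO hospitals look worse and surgery looks better. The documents do not support that. Section 2.2.1 gives no direction for frailty, and section 2.1.1 says operated patients may be sicker. The two could offset each other.

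**It might also be inferred that the three TTO levels will agree and so confirm each other falsely.** Consultant TTO is partly within-hospital, and the simulated estimates differ by level.

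**Conclusion.** The stated justification covers selection by TTO but not composition of catchments, and no contrast described in the protocol holds the hospital fixed. The gap is worth closing because the estimator magnifies small imbalances: 0.1 point of residual difference becomes 0.5 to 2.3 points, depending on condition.

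These sizes rest on assumed values of d, a constant treatment effect, and trust-level pilot ranges from one year. The primary instrument is hospital-level by financial year, whose spread is not given. The simulation shows the mechanism under assumed correlations and is not an estimate for HES.

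A reader might conclude that TTO is invalid or that the primary result will be biased. The documents do not show that: no residual catchment difference is demonstrated, and the pilot balance is mildly reassuring. The finding is an incomplete argument and a missing direct check, both of which can be put right before analysis.

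**What to change.** 1. **Reword the independence paragraph** in Checking IV assumptions. Keep local attendance as support for the absence of selection by TTO, where it is a valid point, and name unmeasured differences between catchments as the remaining threat.
2. **Add region to the covariates.** This removes differences between regions but not between catchments within a region.
3. **Run the planned consultant-level sensitivity analysis a second time with hospital-by-financial-year effects.** Calculate consultant TTO from the consultant's other years, so that it excludes the patient's own treatment and same-year cases. Report instrument strength, and covariate balance between consultants within hospital, because allocation to consultants needs its own check.
4. **Report it beside the primary hospital-level result as supporting evidence.** It should not be a pass/fail rule for robustness: the protocol chose hospital level because multidisciplinary input informs the decision, and the within-hospital instrument is weaker.

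Consultant, hospital and year are already identified in HES, so the cost is extra model terms and one extra TTO calculation. The within-hospital intervals will be wider, consultants with a single year of data drop out, and a preference stable across years must be assumed. For rarer conditions such as hernia it will add little information.
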